NON-INTERVENTIONAL (NI) STUDY PROTOCOL

Study information

Title	Coronavirus Disease 2019 (COVID-19) Vaccination and Breakthrough Infections Among Persons with Immunocompromising Conditions in the United States
Protocol number	C4591035
Protocol version identifier	1.0
Date	25 August 2021
EU Post Authorization Study (PAS) register number	Study is not a post-approval safety study (PASS) and is not registered Date assessed: 09 August 2021
Active substance	Tozinameran
Medicinal product	Research name: BNT162b2 Brand name: Comirnaty
Research question and objectives	Primary Objectives Aim 1: Describe profiles, vaccine utilization and resource use among subjects with immunocompromising (IC) conditions vaccinated with BNT162b2 Aim 2: Evaluate incidence rates of breakthrough infections among subjects with IC conditions fully vaccinated with BNT162b2 Aim 3: Evaluate the clinical presentation of vaccine breakthrough cases among subjects with IC conditions, including time to infection and severity of disease (hospitalization, mortality)

PFIZER CONFIDENTIAL

[REDACTED]

[figure not shown]
	
Secondary Objectives
 
Evaluate Aims 1, 2, 3 and healthcare resource utilization (HCRU) / costs over time and stratified by relevant patient characteristics (eg, age), in specific IC conditions and by vaccination type (eg, any Messenger ribonucleic acid (mRNA)).
 
Exploratory Objective
 
Generate early estimates of the effectiveness of BNT162b2 in preventing COVID-19 infection, stratified by relevant patient characteristics (eg, age) and in specific IC conditions.
 
While the analyses will be focused on the IC population, analyses will also be conducted (in part or entirely) on the non-IC population, the total (IC + non-IC) population or relevant subgroups (eg, other high-risk conditions, vaccination status) to support the interpretation of findings.

Author	PPD (see section below for full list of study investigators)

This document contains confidential information belonging to Pfizer. Except as otherwise agreed to in writing, by accepting or reviewing this document, you agree to hold this information in confidence and not copy or disclose it to others (except where required by applicable law) or use it for unauthorized purposes. In the event of any actual or suspected breach of this obligation, Pfizer must be promptly notified.

2. LIST OF ABBREVIATIONS

Abbreviation	Definition
ACE	Angiotensin Converting Enzyme Inhibitors
AIDS	Acquired Immunodeficiency Syndrome
ARB	Angiotensin-Receptor Blockers
CDC	Centers for Disease Control and Prevention
CDM	Charge Description Master
CI	Confidence Interval
CKD	Chronic Kidney Disease
CNS	Central Nervous System
COVID-19	Coronavirus Disease 2019
CPT-4	Current Procedural Terminology, 4th Edition
ECMO	Extracorporeal Membrane Oxygenation
ED	Emergency Department
ENCEPP	European Network of Centres for Pharmacoepidemiology and Pharmacovigilance
ESRDEUA	Emergency Use Authorization
FDA	US Food and Drug Administration
GPP	Guidelines for Good Pharmacoepidemiology Practices
HCPCS	Healthcare Common Procedure Coding System
HCRU	Healthcare Resource Utilization
HIPAA	Health Insurance Portability and Accountability Act

PFIZER CONFIDENTIAL

HIV	Human Immunodeficiency Virus
IC	Immunocompromising
ICD	International Classification of Diseases
ICD-10-CM	International Classification of Diseases, 10 th Revision, Clinical Modification
ICD-10-PCS	International Classification of Diseases, 10 th Revision, Procedure Coding System
ICU	Intensive Care Unit
IEC	Independent Ethics Committee
IgA	Immunoglobulin A
IgG	Immunoglobulin G
IM	Immuno-Modulators
IMV	Invasive Mechanical Ventilation
IRB	Institutional Review Board
IS	Immunosuppressive
ISPE	International Society for Pharmacoepidemiology
J&J	Johnson & Johnson
LOS	Length of Stay
mRNA	Messenger Ribonucleic Acid
N	Number
N/A	Not Applicable
NDC	National Drug Code
NEC	Not Elsewhere Classified
NOS	Not Otherwise Specified

PASS	Post-Approval Safety Study
PCS	Procedure Coding System
PCV	Proportion of Subjects with Breakthrough SARS-CoV-2 Infections that are Vaccinated
PV	Proportion of the Population that is Vaccinated
Q1	First Quartile
Q3	Third Quartile
QC	Quality Check
RCT	Randomized Controlled Trial
RTIE	Real-Time Insights and Evidence
SARS-CoV-2	Severe Acute Respiratory Syndrome Coronavirus 2
SD	Standard Deviation
STROBE	Strengthening the Reporting of Observational Studies in Epidemiology
US	United States
VE	Vaccine Effectiveness
Vx	Vaccine
WBCs	White Blood Cells
WHO	World Health Organization

4. AMENDMENTS AND UPDATES

None.

PFIZER CONFIDENTIAL

5. MILESTONES

Milestone	Planned date
Draft study protocol	09 August 2021
Final study protocol	20 August 2021
Internal compliance and registration (Quality check (QC), ct.gov)	09 August 2021 – 24 August 2021
Start of data analysis	25 August 2021 (anticipated)
End of data analysis	30 December 2021
Final study report	Interim: 23 September 2021 Final: 28 January 2022

6. RATIONALE AND BACKGROUND

In December of 2019, the first cluster of cases of coronavirus disease 2019 (COVID-19), caused by severe acute respiratory syndrome coronavirus 2 (SARS-CoV-2) infection, were reported to the World Health Organization.¹ By the end of 2020, the number of COVID-19 cases in the United States had reached 20,402,814 with 369,742 deaths attributed to the illness.² In December 2020 two vaccines were issued Emergency Use Authorization (EUA) by the United States (US) Food and Drug Administration (FDA) for active immunization to prevent COVID-19: BNT162b2 (Pfizer/BioNTech) and mRNA1273 (Moderna).^{3,4} A third vaccine (Ad26.COV2.S, Janssen) was issued EUA on 27 February 2021.⁵ These three vaccines demonstrated efficacy in randomized controlled trials (RCTs) against COVID-19 illness, including severe disease; the mRNA vaccines demonstrated efficacies of 94% to 95% in preventing symptomatic COVID-19 illness.⁶ At the time of this study, the mRNA vaccines were the most widely administered in the US and evidence is accumulating under real-world conditions that they are highly effective for protecting against SARS-CoV-2 infection, symptomatic COVID-19 illness, and COVID-19-related hospitalization and death, with findings generally consistent with the RCTs.⁶

As vaccination coverage continues to increase across the US and in other countries, it is important to understand vaccine effectiveness (VE) in subpopulations, especially those who were under-represented in RCTs, may have suboptimal immune responses to vaccines, and may be at higher risk for COVID-19-related complications, such as those persons with an immunocompromising (IC) condition.^{7,8} There is emerging real-world evidence that people with an IC condition may not develop as a robust of an immune response as the general population to COVID-19 vaccines and are at increased risk of poor outcomes.⁸⁻¹² Currently, there is sparse information in the published literature on whether suboptimal generation of an

immune response to the COVID-19 mRNA vaccines in people with an IC condition leads to reduced VE. In the RCTs of the mRNA vaccines, those with an IC condition were largely excluded from the study populations.^{13, 14} A few recently conducted real-world studies that contained subpopulations with IC conditions have found that while the COVID-19 vaccines were effective in this patient group, VE against SARS-CoV-2 infection, symptomatic illness, and COVID-19-related hospitalization was lower than observed in the general populations of these studies.¹⁵⁻²³

On 12 August 2021, the FDA amended the EUA for the mRNA COVID-19 vaccines to allow for the use of an additional dose for certain immunocompromised subjects with moderate to severe IC conditions. According to the Centers for Disease Control and Prevention (CDC) guidelines (COVID-19 Vaccines for Moderately to Severely Immunocompromised People | CDC), the additional dose should be administered at least 28 days following the two-dose regimen of the same vaccine to individuals 18 years of age or older (ages 12 or older for Pfizer-BioNTech) who have undergone solid organ transplantation, or who are diagnosed with conditions that are considered to have an equivalent level of immunocompromise. A third dose of the same Mrna vaccine should be used; however, if the Mrna vaccine product given for the first two doses is not available or is unknown, either Mrna COVID-19 vaccine product may be administered.

Further study of patients with various IC conditions is warranted to gain a better understanding of which IC conditions may predispose people to reduced COVID-19 VE to guide further prevention efforts.

7. RESEARCH QUESTION AND OBJECTIVES

The overall objective of this study is to evaluate characteristics, vaccine utilization and outcomes among vaccinated subjects with IC conditions. The primary analysis will be conducted on subjects vaccinated with BNT162b2. A variety of subgroup analyses are planned, along with multiple sensitivity analyses that will test how variations in study design affect results.

Primary Objectives:

Aim 1: Describe profiles, vaccine utilization and resource use among subjects with IC conditions vaccinated with BNT162b2

Aim 2: Evaluate incidence rates of breakthrough infections among subjects with IC conditions fully vaccinated with BNT162b2

Aim 3: Evaluate the clinical presentation of vaccine breakthrough cases among subjects with IC conditions, including time to infection and severity of disease (hospitalization, mortality)

Secondary Objectives

Evaluate Aims 1, 2, 3 and HCRU/costs over time and stratified by relevant patient characteristics (eg, age), in specific IC conditions and by vaccination type (eg, any Mrna).

Exploratory Objective

Generate early estimates of the effectiveness of BNT162b2 in preventing COVID-19 infection, stratified by relevant patient characteristics (eg, age), in specific IC conditions.

8. RESEARCH METHODS

8.1. Study design

This study will be a retrospective database analysis utilizing data sets within the HealthVerity database (Philadelphia, Pennsylvania) covering the time period 01 December 2018 through 08 July 2021 (or latest data available) to describe the characteristics of subjects with IC conditions vaccinated with BNT162b2 and to evaluate the incidence of SARS-CoV-2 breakthrough infections.

Study period: 01 December 2018 – 08 July 2021 (or latest data available)

Index identification period: 11 December 2020 – 08 July 2021 (or latest data available; inclusive)

Index date: The first record for a SARS-CoV-2 vaccine (primary analysis: BNT162b2; sensitivity analyses: any Mrna, any authorized vaccine) from a medical claim, pharmacy claim, or chargemaster record.

Baseline period: 12-month period prior to the index vaccination date

Follow-up period: Variable period beginning after the index date and continuing until the earliest of the following: end of the study or end of continuous insurance enrollment.

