Prevention seeking behavior (at baseline)	Patient Characteristics	HealthVerity Vaccine Data	
These variables will be assessed during the 12 month baseline period:
 
Telephone or Telehealth visits defined as a claim with any of the following procedure codes (G2012, G2010, G2061-G2063; 99205-99205, 99212-99215, 99421-99423, 99441-99443, G0425-G0427, G0406-G0408)
 
COVID-19 laboratory tests defined as a claim with any of the following CPT-4 codes (87635, 86318, 86328, 86769, 87426, 86408, 86409, 86413)
 
Flu vaccinations defined as a claim with the following procedure codes (90653-90664, 90666-90668, 90724, 90470, 90672, 90673, 90685-90688)
 
The cumulative proportion of IC and non-IC subjects receiving their first dose of COVID-19 vaccine, by month, starting from December 2020 until most recent data.

Acute Respiratory Infection Hospitalization (at baseline)	Patient Characteristics	HealthVerity Vaccine Data	Any inpatient claim that occurs in the 12 month baseline period with a diagnosis of J00-J06, J09-J18, J20-J22 will be reported
Follow-up time	Patient Characteristics	HealthVerity Vaccine Data	The number of days between the index date and the earliest of the following: end of the study or end of continuous insurance enrollment
IS drugs use	Patient Characteristics	HealthVerity Vaccine Data	The proportion of subjects with IC conditions and usage of IS drugs for >14 days during the baseline period will be reported, as well as use within 14 days and 28 days within receipt of the first vaccine dose. IS drugs exclude low-dose [<60mg/day] prednisone.

PFIZER CONFIDENTIAL

Table 3. Patient Characteristics and Vaccine Utilization variable definitions

Variable	Role	Data source(s)	Operational definition
COVID-19 supportive medication use	Patient Characteristics	HealthVerity Vaccine Data	The use of medications considered supportive for COVID-19 will be assessed in the 12-month baseline period including remdesivir, dexamethasone, doxycycline, norepihephrine, methylprednisolone, lopinavir/ritonavir, eculizumab, sarilumab, tocilizumab, losartan, azithromycin, hydroxychloroquine, siltuximab, colchicine, and convalescent plasma. Codes used to identify these treatments will be based on the Sentinel COVID-19 Natural History Master Protocol

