Intensive Care Unit (ICU)	Outcome	HealthVerity Vaccine Data	A claim with a procedure code indicative of ICU utilization during a hospitalization that occurs after the breakthrough COVID-19 diagnosis or at the same time/episode of care 1 st admission and readmissions will be differentiated.
Invasive Mechanical Ventilation (IMV) / Extracorporeal Membrane Oxygenation (ECMO)	Outcome	HealthVerity Vaccine Data	A claim with a procedure code indicative of IMV/ECMO utilization during a hospitalization that occurs after the breakthrough COVID-19 diagnosis or at the same time/episode of care Includes both 1 st admission and readmissions.
Inpatient Death	Outcome	HealthVerity Vaccine Data	Death that occurs on or after the date of the breakthrough COVID-19 diagnosis. The date of death will be assumed to be the same as the date of the last recorded encounter in the database.

PFIZER CONFIDENTIAL

Table 5. COVID-19 Healthcare resource use and Costs definitions

Variable	Role	Data source(s)	Operational definition
			
Death information is available from the Charge Description Master (CDM) data and is provided as year-month of death only.
 
Time to death will also be explored.

Length of Stay (LOS)	Outcome	HealthVerity Vaccine Data	
Length of stay (LOS) associated with different types of hospitalization treatments mentioned above (eg, ICU), applicable for first index hospitalization and/or readmissions.

Costs	Outcome	HealthVerity Vaccine Data	
Non-zero costs associated with any of the previously listed Outpatient and Inpatient encounters (but death).
 
Charges may be assessed in sensitivity analyses to interpret the cost data.

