8.6. Data management

This study will use secondary data collected in the HealthVerity Healthcare database, specifically from the Vaccine and Real-Time Insights and Evidence (RTIE) data sets, which are de-identified and HIPAA compliant. The study will utilize a data cut consisting of data from December 1, 2018 through July 8, 2021 (or the most recent data available).

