8.7. Data analysis

Data analyses will follow extensive feasibility analyses aimed at determining whether a full study and the assessment of vaccine effectiveness are feasible, as illustrated below:

Study implementation approach

Characteristics of the IC, non-IC and total population (IC + non-IC) groups will be described. Descriptive statistics for continuous variables will include N (number of patients), mean, median, standard deviation, Q1, Q3, minimum, and maximum. Categorical variables will be described using frequency counts and percentages.

The incidence rate of breakthrough cases of SARS-CoV-2 infection will be determined based on the following:

- Among fully vaccinated patients, those who have a claim for COVID-19 (ICD-10-CM: U07.1) that occurs on or after >14 days following their second dose of an mRNA vaccine (or 1st dose of Johnson & Johnson) will be considered to have had a breakthrough event. The time from 14 days after the qualifying dose until the breakthrough event will be the person time at risk.

PFIZER CONFIDENTIAL

- Among fully vaccinated patients with no evidence of COVID-19 after their qualifying dose, the time from 14 days after the qualifying dose until the end of follow-up will be the person time at risk.

[figure not shown]
The incidence rate of breakthrough cases of SARS-CoV-2 infection will be calculated as the number of patients who experience the event divided by the observed time at risk, and reported per 100 person years. Poisson 95% confidence intervals will be reported for the incidence rates.

Absolute effect measures such as risk difference between non-IC and IC will be reported. Time period specific effect estimates (eg, at 6 months after vaccination) may be estimated if feasible. The characteristics of the breakthrough infections will be described, including clinical presentation and severity.

The primary analysis will describe results among the non-IC cohort and the IC cohort who are vaccinated with BNT162b2. Subgroup analyses will include results for clinically meaningful subgroups as defined by vaccination type, relevant patient characteristics (eg, age), and each IC condition as listed below:

- HIV/AIDS
- Solid malignancy
- Bone marrow transplant
- Organ transplant (excluding bone marrow)
- Rheumatologic/inflammatory
- Primary Immunodeficiencies
- Other immune condition
- CKD or ESRD
- Hematologic malignancy

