- IS drug use: >14 days IS medications (chemotherapy, immuno-modulators (IM), or corticosteroids excluding low-dose [<60mg/day] prednisone – See Drug List) and not falling into any of the above 9 condition groups
- >14 days of anti-metabolite use and not falling into any of the above 10 condition or drug use groups
- More than 1 IC condition

PFIZER CONFIDENTIAL

Analyses for younger cohorts (eg, 12-15) will also be conducted, as data accumulates.

For the exploratory aim, the Screening Method will be used to calculate VE for the overall study population of subjects with an IC condition and also stratified VE estimates for the different immunocompromised subject groups, with VE also determined for those subjects with >1 IC condition²⁶. We will use the proportion of the population that are vaccinated (PV) and the proportion of subjects with breakthrough SARS-CoV-2 infections that are vaccinated (PCV) to calculate VE using the following formula:

$$VE = (PV - PCV) / [PV(1-PCV)]$$

where PV = the proportion of the population that is vaccinated (ie, vaccination coverage) and PCV = the proportion of subjects with breakthrough SARS-CoV-2 infections that are vaccinated.

Additionally, breakthrough incidence rates and VE will be stratified by age at diagnosis (eg, < 65 and \geq 65 years of age at index vaccination).

Sensitivity analyses will be conducted to test the robustness of findings by varying key study design aspects (eg, continuous enrolment, IC case definition) and data analysis techniques. Other statistical techniques (eg, matched analyses, multiple regression, propensity scores) may be applied on an exploratory basis after careful examination of potential confounders (eg, age, time from vaccination). Exploratory analyses related to alternate dosing may also be conducted upon feasibility results, and as recommendations from public health authorities evolve. The analyses (entirely or in part) will be conducted over time and updated on a rolling basis as monthly data cuts become available.

While the analyses will be focused on the IC population, analyses will also be conducted (in part or entirely) on the non-IC population, the total (IC + non-IC) population or relevant subgroups (eg, other high-risk conditions, vaccination status) to support the interpretation of findings.

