8.8. Quality control

Data in HealthVerity's COVID Healthcare database are collected weekly in an electronic format. HealthVerity employs its foundational product to match patients between different data sources with high accuracy. However, not all data points are available in every data source and as a result, not all variables in the database are completely populated. In addition, the database contains both pre- and post-adjudicated claims and, based on the data source, adjudication may or may not be captured. To maximize data completeness and uniformity, it may be necessary to exclude certain data sources from the analysis due to differences in data structure and content.

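### Time at risk has no stated claims run-out and does not end at death, so the Aim 2 breakthrough rates are likely understated, by an amount the documents cannot fix

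*Combined protocol and SAP*

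**What the plan says.** Section 8.1 ends follow-up at whichever comes first of two events: "continuing until the earliest of the following: end of the study or end of continuous insurance enrollment". Table 3 in section 8.3 defines follow-up time by the same two events: "The number of days between the index date and the earliest of the following: end of the study or end of continuous insurance enrollment". The study end is 8 July 2021 or the latest data available (sections 8.1 and 8.6).

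For fully vaccinated patients with no COVID-19 claim, section 8.7 says "the time from 14 days after the qualifying dose until the end of follow-up will be the person time at risk". The breakthrough rate is "the number of patients who experience the event divided by the observed time at risk, and reported per 100 person years", with Poisson 95% confidence intervals. An event is a U07.1 claim more than 14 days after the second dose (Table 4).

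Section 8.8 notes that "the database contains both pre- and post-adjudicated claims". Section 8.7 says the analyses will be "updated on a rolling basis as monthly data cuts become available". Death appears only in Table 5, as an inpatient outcome following a breakthrough. It comes from chargemaster data, is "provided as year-month of death only", and is dated to the last recorded encounter. The milestones in section 5 put the start of analysis at 25 August 2021.

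**The concern.** The numerator depends on claims that take time to arrive, whereas the denominator accrues by the calendar. If follow-up runs right up to a receipt-date cut, the last weeks contribute person-time in full but only part of their events. Time at risk here is short, so a few weeks is a large share of it.

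Aim 2 is a primary objective, and section 8.7 names an absolute contrast between the non-IC and IC cohorts. A common proportional loss in both rates shrinks that contrast by the same proportion. The secondary objective looks at results over time, where an apparent fall just before each cut could be read as a real one.

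Death raises a related problem. Unless enrollment closes at death, a patient who has died keeps adding time at risk. Such a patient could even satisfy the requirement in Table 2 for more than 14 days of follow-up after dose 2 without having lived that long.

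**Working it through.** The plan states no lag, expected rate, event count or sample size, so there is no figure of its own to reproduce. The calculation shows what the rule implies under stated assumptions.

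**Dates from the documents.** 11 December 2020 to 8 July 2021 is 209 days. 8 July to 25 August 2021 is 48 days.

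**Assumptions, not in the documents.** A 21-day gap between doses, so the longest time at risk is 209 − 21 − 14 = 174 days; times at risk T spread evenly over 1 to 174 days (mean 87.5); a constant, low hazard; exponential claim lag with mean L; annual mortality m.

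**Run-out.** An event s days before the cut is visible with probability 1 − exp(−s/L). A person at risk for T days then loses the equivalent of L(1 − exp(−T/L)) days of event capture. Dividing the average loss by 87.5 gives the shortfall. If the data are extracted 48 days after a service-date cut, the loss is L(exp(−48/L) − exp(−(T+48)/L)).

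| Mean lag L (days) | Average loss, no run-out (days) | Rate low by, no run-out | Rate low by, 48 days of run-out |
|---|---|---|---|
| 7 | 6.74 | 7.7% | 0.0% |
| 14 | 12.91 | 14.8% | 0.5% |
| 30 | 24.93 | 28.5% | 5.8% |
| 45 | 33.73 | 38.6% | 13.3% |

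**Death.** The share of counted person-time that falls after death is 1 − (1 − exp(−mT))/(mT), with T in years.

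| Annual mortality m | T = 90 days | T = 174 days |
|---|---|---|
| 1% | 0.12% | 0.24% |
| 5% | 0.61% | 1.2% |
| 10% | 1.2% | 2.3% |
| 20% | 2.4% | 4.6% |

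**Effect on the cohort contrast.** Take illustrative true rates of 2 (IC) and 1 (non-IC) per 100 person-years, the same spread of times at risk in both cohorts, and mortality of 10% and 1% over 90 days (death factors 0.988 and 0.999). The share of events retained is 0.852 at L = 14 and 0.715 at L = 30.

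- L = 14: 2 × 0.852 × 0.988 − 1 × 0.852 × 0.999 = 0.83, against a true difference of 1.00.
- L = 30: 2 × 0.715 × 0.988 − 1 × 0.715 × 0.999 = 0.70.
- Ratio in both cases: 2 × 0.988/0.999 = 1.98, against a true 2.00.

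**What ending follow-up earlier would achieve.** With no other run-out, stopping 30 days before the cut cuts the shortfall from 14.8% to 2.1% (L = 14) and from 28.5% to 12.1% (L = 30). Stopping 60 days before leaves 0.3% and 5.3%.

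**The case against.** The plan is silent on run-out, which is not the same as having none. If 8 July is a service-date cut and the extract was taken near 25 August, the 48 days between them do most of the work for lags up to a month. Pre-adjudicated claims, weekly collection (section 8.8) and nearly real-time data (section 8.4) all point to a short lag. Late second-dose claims keep some recent vaccinees out of the denominator as well, so the denominator is not fully complete either. Later cuts fill in earlier weeks, and section 8.7 promises sensitivity analyses on design aspects. Enrollment may in practice close at death.

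Much of this stands, and it limits the size. It does not close the gap. Sections 8.1 and 8.6 allow the latest available data in place of 8 July, which could remove the 48 days, and each rolling update raises the question again. The sensitivity analyses name continuous enrollment and the IC definition as examples, but neither lag nor death. Section 8.9 concedes underreporting in general, not claim lag. The plan does not say how the end of enrollment is derived.

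A reader might infer that no breakthrough could be recorded in the final weeks. That is true only after death; during the lag, events are under-captured. A reader might also infer that the IC/non-IC ratio is biased because one cohort was vaccinated later. The documents give neither cohort's vaccination timing. Even with assumed times at risk spread evenly over 46–174 days (IC) and 0–160 days (non-IC), and half the claims missing in the last 60 days, the losses are about 27% and 30%, and the ratio is inflated only by a factor of about 0.73/0.70, or roughly 1.05.

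**Conclusion.** The point holds as a gap in the end-of-follow-up rule, with a likely downward direction and an unknown size. Followed as written on a latest-available cut, the rule counts time during which claims are still arriving, and counts time after death wherever enrollment remains open.

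The run-out part could be material or close to nothing, depending on the type of cut and the lag, and the documents give neither the cut type nor the lag. The ranges above rest on the assumed lag distribution, dose gap and spread of times at risk. The death part is minor: usually about 2% or less of person-time, and just under 5% in the most extreme case considered. The absolute IC versus non-IC difference shrinks along with the rates. Distortion of the ratio is not shown and is small if the cohorts have similar times at risk. The documents do not support saying flatly that the rates are too low, or that the cohort comparison is biased in relative terms.

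**What to change.** In sections 8.1 and 8.7 and in Table 3:

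- State whether each cut is by service date or receipt date, and when the extract is taken.
- End follow-up at the earliest of end of enrollment, death, or the cut minus a fixed interval. Take the interval from the delay between service date and first appearance of U07.1 claims across the monthly cuts. Set it to zero if the extract already includes adequate run-out.
- Report the Aim 2 rates with follow-up ended 30 and 60 days earlier as a sensitivity analysis.
- State how the month-only death date is turned into a censoring date, and that deaths outside the chargemaster source will be missed. Censoring at death will therefore be incomplete.

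The text change is a few lines and uses data already held. The cost is recent person-time: under the even 1–174 day spread, about 69% is kept when follow-up ends 30 days earlier and 43% at 60 days. The primary interval should therefore be no longer than the observed lag requires.
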